Sample Size: Approximately 90 patients will be enrolled in the study. The planned number of patients within each tumor-specific cohort is as follows: CRC (N = 20), OvC (N = 20), SCLC (N = 20), TNBC (N = 15), and AML (N = 15). This study uses a Bayesian monitoring approach to guide decision-making using data on the primary efficacy endpoint (ORR for patients in the solid tumor arms and rate of achievement of CR/CRi/CRp in patients in the AML arm) within each tumor-specific cohort. If the data provide high confidence that the true ORR (or CR/CRi/CRp rate for AML) exceeds a minimal clinically meaningful level or threshold, then the results would support continued development (a “Go” decision) for that cohort. If the data suggest that the true ORR (or CR/CRi/CRp rate for AML) is unlikely to meet the desired level of clinical activity, then the results would support a decision to halt further continuation of accrual (a “Stop” decision) for that cohort. This approach is

based on the decision-making framework of [Lalonde et al, 2007](#) and [Frewer et al, 2016](#).

For each tumor type test, the minimal clinically meaningful level of any given ORR (or CR/CRi/CRp rate for AML) value/result is defined by the “lower reference value” (LRV), and the desired level of clinical activity is defined by the “target value” (TV). The LRV and TV for each tumor type are determined by a synthesis of medical opinion, evidence from the literature, or data from other compounds being developed in the same area. These values are as follows: CRC LRV=10%, TV=20%; OvC LRV=10%, TV=20%; SCLC LRV=30%, TV=40%; TNBC LRV=15%, TV=25%; AML LRV=15%, TV=25%.

Enrollment in a cohort may be stopped for futility prior to reaching the planned sample size if there is a high predicted probability of a Stop decision at the planned sample size. Enrollment in a cohort may be increased with approximately 10 additional patients beyond the planned sample size if the sponsor determines that further data is needed to clarify the safety or efficacy signals for a Go/No-Go decision.

Based on the performance characteristics computed and described in the statistical section of the protocol, the sample sizes are adequate to address the study’s objectives. No formal statistical power calculations to determine sample size were performed.

Statistical Methods:

Analysis Sets

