- The full analysis set (FAS) comprises all patients who are assigned to receive study treatment as per the intent-to-treat (ITT) principle, regardless of whether or

not they subsequently go on to receive study treatment or whether they deviate from the protocol in any major way.

- The modified intent-to-treat (mITT) set comprises all patients who are assigned to receive study treatment and have at least 1 post-baseline efficacy assessment (RECIST 1.1), even if they deviate from the protocol in any major way. The mITT will also include any patient that goes off study treatment because of clinical progression prior to the first scheduled per-protocol scan.
- The safety analysis set comprises all patients who receive any amount of study drug.
- The per-protocol set (PPS) comprises all patients who are assigned to receive study treatment, receive at least 1 injection of study treatment, have at least 1 post-baseline efficacy assessment (RECIST 1.1), and do not deviate from the protocol in any major way

All efficacy analyses will be based on the FAS and will also be conducted on the mITT set and PPS for exploratory purposes. The study's primary objective will be judged on the basis of the analysis of ORR. For CRC patients, only those with MSS and MSI-L will be included in the primary efficacy analysis. The safety analyses will be based on the safety analysis set and will group patients according to treatment actually received. Secondary and exploratory efficacy analyses will be performed on the FAS as well as on the mITT set and PPS for exploratory purposes.

Analysis of Primary Efficacy Endpoint: For each tumor-specific cohort, a Bayesian approach with non-informative

Jeffreys prior beta distribution with parameters $a = 0.5$ and $b = 0.5$ will be used to estimate the ORR (or CR/CRi/CRp rate in AML) and its 95% credible interval based on the posterior distribution.

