- i. The serum chemistry assessments will include sodium, potassium, chloride, carbon dioxide, blood urea nitrogen, creatinine, calcium, total protein, albumin, glucose, total bilirubin, alkaline phosphatase, aspartate aminotransferase, alanine aminotransferase, and lactate dehydrogenase. These samples will be collected for processing by the central laboratory. Samples must be collected before study treatment administration. Calculated Creatinine Clearance (CrCl) must be assessed during the screening period to determine eligibility. See the laboratory manual for more information.
- j. Urine dipstick testing will be performed locally at the site.
- k. Patients will provide any historical documentation of HLA type at the pretreatment screening visit. The majority of patients will not have such information available and must undergo HLA typing assessment at participating sites.
- l. ***For AML patients ONLY:*** provide historical documentation of cytogenetic and molecular analyses results (from initial diagnosis) at the pretreatment screening visit. Only patients with abnormal karyotype at initial diagnosis will require to repeat karyotype plus/minus fluorescence in situ hybridization (FISH) at pretreatment screening in this study. Full molecular analysis (i.e., FLT3-ITD and NPM1 mutations, etc.) will also be performed on bone marrow biopsy samples collected during pretreatment screening in all AML patients.
- m. ***For AML patients ONLY:*** a bone marrow aspiration and biopsy is required during pretreatment screening to confirm morphologic partial response (PR) or stable disease (SD) status, for MRD analysis, and for cytogenetic and molecular analyses as defined in footnote k. Additional bone marrow biopsies are required as shown per schedule, as well as at the end-of-treatment/early termination visit to evaluate progression and MRD. If a peripheral blood differential result (including manual differentiation) at any study visit is suggestive of abnormal or immature cells and a possible relapse, a bone marrow biopsy must be performed as part of a scheduled AML relapse visit. If the bone marrow biopsy confirms relapse, the patient will be discontinued from the study and will need to return to the site 0 to 30 days after their last treatment injection for end-of-treatment/early termination procedures. The bone marrow aspiration performed as part of the scheduled relapse visit will serve as bone marrow aspiration procedure required at the end-of-treatment/early

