
termination visit. A bone marrow biopsy must be collected if an adequate aspiration is not attainable. Refer to the laboratory manual for collection and processing these samples.

- ⁿ. ***For AML patients ONLY***: Analysis of MRD will be performed on samples of peripheral blood and will be evaluated by molecular analysis of transcripts. Peripheral blood samples will be collected from patients according to the schedule shown. Samples must be collected before study treatment administration. Refer to the laboratory manual for collection and processing of samples.
- ^o. Peripheral blood samples for immunologic response (IR) assessment will be collected from a large subset of patients enrolled in each of the 5 arms of the study at select sites as per the schedule shown. The study is aiming to analyze IR profile in at least 50% of the enrolled patients. Samples must be collected before study treatment administrations. Refer to the laboratory manual for collection and processing these samples.
- ^p. Biopsies of malignant tissue deposit (or bone marrow, for AML patients) will be performed according to the schedule shown in a subset of patients at select sites. These tissue specimens will be used to study the presence and kinetics of host immunocytes infiltrating the above tissues, as well as the expression of key markers of immune biological significance in the tumor microenvironment. All biopsies are in principle mandatory, as long as the tumor deposits are technically accessible and such biopsies can be conducted safely.
- ^q. For solid tumors only: CT or MRI staging assessment (both per RECIST and iRECIST).
- ^r. Prior to contacting IWRS to enroll a patient into the study and obtaining a patient number, the following must be reviewed and verified: inclusion/exclusion criteria (including specific tumor histologic type verification, [e.g., TNBC]), laboratory and tissue pathology.
- ^s. GM-CSF will be administered 2 days before and on the day of each galinepimut-S administration. A GM-CSF dose of 70 µg will be injected subcutaneously at the same anatomical site as the planned subsequent galinepimut-S injection (to be given during the same cycle of therapy). Before injection, study staff should assess the immunization site. On Day -1, patients will remain in the clinic for approximately 30 minutes following receipt of GM-CSF to monitor for any adverse reactions. Blood samples will be collected before study treatment administration.

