6.2. Efficacy Assessments

Signal response for each a priori statistically defined clinical outcome (ORR per RECIST 1.1) for all patients enrolled in the solid tumor arms of the study or other appropriate instruments scales, such as attainment of morphologic CR in patients enrolled in the AML arm. In addition to RECIST 1.1, all scans will be read according to iRECIST immune response consensus guideline ([Seymour et al, 2017](#)) to ensure that patients are not discontinued from therapy due to the phenomenon of tumor “pseudoprogression”, and clinical decisions will be based on iRECIST ([Hodi et al, 2016](#)). ORR per iRECIST will be an exploratory endpoint of this study.

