6.8.2. Tumor Imaging During the Study

For solid tumors only, the first on-study imaging assessment should be performed at Week 9 (Day 1 \pm 7 days) from the date of enrollment. Subsequent tumor imaging should be performed at Weeks 18, 27, 36, 45, 54, 63, 72, and 84 (Day 1 \pm 7 days) or more frequently if clinically indicated. Imaging timing should follow calendar days and should not be adjusted for delays in cycle starts. Imaging should continue to be performed until disease progression is identified by the investigator.

Objective response should be confirmed by a repeat imaging assessment. Tumor imaging to confirm PR or CR should be performed at least 4 weeks after the first indication of a response is observed. Patients will then return to regular scheduled imaging, starting with the next scheduled imaging time point. Patients who receive additional imaging for confirmation do not need to undergo the next scheduled tumor imaging if it is less than 4 weeks later; tumor imaging may resume at the subsequent scheduled imaging time point.

Per iRECIST ([Section 6.8.5](#)), disease progression should be confirmed by the site 4 to 8 weeks after.

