7.5. Analysis Sets

- The full analysis set (FAS) comprises all patients who are assigned to receive study treatment as per the ITT principle, regardless of whether or not they subsequently go on to receive study treatment or whether they deviate from the protocol in any major way.

- The modified intent-to-treat (mITT) set comprises all patients who are assigned to receive study treatment and have at least 1 post-baseline efficacy assessment (RECIST 1.1), even if they deviate from the protocol in any major way. The mITT will also include any patient that goes off study treatment because of clinical progression prior to the first scheduled per-protocol scan.
- The safety analysis set comprises all patients who receive any amount of study drug.
- The per-protocol set (PPS) comprises all patients who are assigned to receive study treatment, receive at least 1 injection of study treatment, have at least 1 post-baseline efficacy assessment (RECIST 1.1), and do not deviate from the protocol in any major way.

All efficacy analyses will be based on the FAS and will be conducted on the mITT set and PPS populations for exploratory purposes. For CRC patients, only those with MSS and MSI-L will be included in the efficacy primary analysis. The safety analyses will be based on the safety analysis set and will group patients according to treatment actually received. Secondary and exploratory efficacy analyses will be performed on the ITT/FAS as well as on the mITT and PPS populations for exploratory purposes.

Major protocol deviations will be defined in more detail in the study statistical analysis plan (SAP), and may include, but not be limited to, incorrect diagnosis and poor compliance.

All analyses using the PPS will group patients according to treatment actually received.

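### The mITT and per-protocol sets are defined by a RECIST 1.1 assessment that AML patients never have, so neither exploratory set works for the AML cohort

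*Combined protocol and SAP*

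**What the plan says.** Section 7.5 defines four analysis sets for the whole study. Both the mITT set and the PPS require that patients "have at least 1 post-baseline efficacy assessment (RECIST 1.1"). The synopsis repeats this; its PPS wording is that patients "have at least 1 post-baseline efficacy assessment (RECIST 1.1), and do not deviate from the protocol in any major way". The mITT has one further route: "The mITT will also include any patient that goes off study treatment because of clinical progression prior to the first scheduled per-protocol scan". The PPS has none. Neither place gives an AML version.

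Imaging is confined to the other four cohorts. Table 8, footnote q, reads "For solid tumors only: CT or MRI staging assessment (both per RECIST and iRECIST"), and Section 6.8.2 reads "For solid tumors only, the first on-study imaging assessment should be performed at Week 9".

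For AML, the synopsis gives the primary efficacy endpoint as "rate of achievement of CR/CRi/CRp in patients in the AML arm", and Section 6.2 names the instrument as "attainment of morphologic CR in patients enrolled in the AML arm". Marrow sampling is planned: Table 8, footnote m, states "Additional bone marrow biopsies are required as shown per schedule", and footnote w puts the first on-treatment sample at Week 9.

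Section 7.5 bases all efficacy analyses on the FAS and commits to repeating them on the mITT set and PPS for exploratory purposes. Section 7.6 says that data are summarized or analyzed by cohort.

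**The concern.** The condition for entering two of the three efficacy populations is an assessment that one of the five cohorts does not undergo. An AML patient in continuing remission meets neither definition, while an AML patient who stops for clinical progression may meet one. The repeat analyses are there to show whether the FAS result holds when unassessed patients or major deviators are set aside. For AML they would instead drop patients who are doing well, or contain nobody. Time to response and duration of response would suffer in the same way: not describable in the AML PPS, and without any ongoing responder in the AML mITT.

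If the wording stands, someone must redefine a prespecified population while programming tables in an open-label, single-arm study, possibly with responses already known.

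**Working it through.** **1. Entry routes for an AML patient, as written**

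| Set | Assessment route | Other route | AML patients admitted |
|---|---|---|---|
| FAS | none required | – | all 15 planned |
| mITT | RECIST 1.1: not available | clinical progression before the first scheduled scan | only patients leaving for clinical progression, with no defined cut-off |
| PPS | RECIST 1.1: not available | none | 0 |

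An incidental CT scan would not help: inclusion criterion 12b requires AML patients to be free of extramedullary disease.

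**2. The plan's own AML figures**

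Inputs from Sections 7.4, 7.6.1 and 7.6.6: N = 15, LRV 15%, TV 25%, Go at 4 or more responses, Stop at 1 or fewer, Beta(0.5, 0.5) prior. Go = P(X ≥ 4) and Stop = P(X ≤ 1), with X ~ Bin(15, p).

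| True rate | Table 13 Go/Consider/Stop (%) | Exact (%) |
|---|---|---|
| 25% | 54/38/8 | 53.9/38.1/8.0 |
| 20% | 35/48/17 | 35.2/48.1/16.7 |
| 15% | 18/50/32 | 17.7/50.4/31.9 |

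Boundaries, from the posterior Beta(0.5 + x, 0.5 + 15 − x):
- Go needs P(rate > LRV) of at least 0.80: 0.726 at 3/15, 0.892 at 4/15.
- Stop needs P(rate > TV) of at most 0.10: 0.037 at 1/15, 0.147 at 2/15.

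Futility, as the beta-binomial predictive probability of Stop against 0.80: 0.789 at 0/5, 0.839 at 0/6, 0.711 at 1/12, 0.804 at 1/13. These give the stated bounds at N of 6 and 13.

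Everything reproduces, and none of it uses the mITT set or PPS.

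**3. What the exploratory sets would show**

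The documents give no AML mITT or PPS figure. As an assumption for illustration, take 4 CR/CRi/CRp among 15 patients and a progression-only mITT of 1 to 6 patients. The Jeffreys posterior mean is (0.5 + x)/(1 + n).

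| Set and reading | x/n | Observed | Posterior mean |
|---|---|---|---|
| FAS | 4/15 | 26.7% | 4.5/16 = 28.1% (95% CrI 9.7–51.7%) |
| mITT, scan read as the first AML response assessment | 0/1, 0/3, 0/6 | 0% | 25.0%, 12.5%, 7.1% |
| mITT, no cut-off, one admitted patient responded and later relapsed | 1/3, 1/6 | 33.3%, 16.7% | 37.5%, 21.4% |
| mITT, nobody admitted | 0/0 | undefined | prior only |
| PPS | 0/0 | undefined | prior only |

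With 0/0 the planned estimator returns the prior: mean 50%, 95% interval 0.2–99.8%.

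**4. Direction of the bias**

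Let r be the true response rate, and let q1 and q0 be the chances that a responder and a non-responder leave for clinical progression. The response rate among patients admitted to the mITT is r·q1 / [r·q1 + (1 − r)·q0]. This is below r whenever q1 < q0. If the scan is read as the first AML response assessment, q1 is 0. Without a cut-off, q1 is positive but excludes every ongoing responder. A very small set can still land above the FAS rate by chance, as 1/3 does here.

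**5. After the correction**

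On the same assumption, the mITT is 4/15 = 26.7% if every patient has a marrow assessment or early clinical progression, and 4/12 = 33.3% if three have neither. The PPS holds up to 15 patients, less those without an assessment or with a major deviation.

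**The case against.** The case on the other side has four parts.

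- **No decision rests on these sets.** Efficacy is based on the FAS, missing response counts as non-response in the primary analysis (Section 7.6.1), and mITT and PPS are labelled exploratory. This stands, and it limits the size of the point.
- **The intent is clear.** Section 6.2 treats morphologic CR as the AML efficacy assessment, so the RECIST reference may be solid-tumor shorthand. That is probably what was meant. But the synopsis adds the AML endpoint expressly where it describes the primary analysis and does not do so in the set definitions. Section 6.2 does not amend them.
- **The SAP may settle it.** Section 7.5 defers the detail of major deviations to the SAP, and Section 7.6 defers methods and data conventions. A separate SAP is not in the combined document, so an AML definition there cannot be ruled out. Neither deferral says that the populations will be redefined.
- **An empty set would be noticed.** Likely for the PPS. A small mITT made up of progressors is easier to overlook.

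Two stronger readings are tempting. A reader might infer that the AML mITT response rate must be 0% whatever the true rate. The text does not support this: AML has no scheduled scan, so the progression clause has no cut-off. It could admit a patient who responded, relapsed and stopped, a course that Section 6.1.5 foresees, or it could admit nobody. Nor is the planned Jeffreys estimate 0% when no responses are seen. A reader might also infer that Go/Stop is compromised, because the synopsis updates the prior with data from evaluable patients. That term is undefined, is not tied to the mITT, and is absent from Section 7.6.1.

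**Conclusion.** The point holds for the exploratory sets. Under the stated definitions the AML PPS has no patients, and the AML mITT is limited to patients who left for clinical progression, with an undefined cut-off. Ongoing AML responders fall outside both. The exploratory AML mITT rate is then biased downward, provided responders leave for progression less often than non-responders, or is undefined if nobody qualifies.

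The extent is one cohort, 15 of 90 planned patients, in two exploratory populations. The primary AML estimate, the Go/Stop criteria, Table 13 and the futility bounds are unaffected. The conclusion assumes that the definitions are applied as written and that no unseen SAP text replaces them.

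**What to change.** In the synopsis and Section 7.5:

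- In both the mITT and PPS definitions, replace *(RECIST 1.1)* with *(RECIST 1.1 for solid tumors; bone marrow morphologic response assessment for AML)*.
- In the mITT progression clause, replace the reference to the first scheduled scan with *first scheduled per-protocol response assessment*. This gives AML a cut-off.

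Carry the same wording into the SAP. The cost is two definitions reworded in each place. Marrow assessments are already scheduled from Week 9, so no new data, visits or patients are needed, and no design figure changes.

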Patients with microsatellite-stable (MSS) tumor genetics make up between 80 to 90% of cases (Naboush et al, 2017; Diaz and Le, 2015). Patients will have microsatellite (MS) instability (MSI) status tested in their primary tumors and will be classified as MSI-high (H) and -low (L) (Pawlik et al, 2004; Morán et al, 2010; Supek and Lerner, 2015; Goldstein et al, 2014). The focus will be on MSI-low tumors, but no entry selection will be applied based on this tumor feature. In several clinical trials in MSI-L CRC, anti-PD-1 agents have shown to induce 0 to 5% ORR (Link and Overman, 2016; <http://www.targetedonc.com/publications/targeted-therapies-cancer/2017/2017-february/immune-checkpoint-inhibitors-in-crc>; Boland and Ma, 2017; Myint and Goel, 2017; Overman et al, 2016; Segal et al, 2016; Bendell et al, 2016; Overman et al, 2016; Andre et al, 2017). This is in contrast to the significant activity of PD1 blockade in MSI-H CRC, the basis for the recent Food and Drug Administration (FDA) approval of pembrolizumab in MSI-H cancers (including CRC) (<https://www.fda.gov/NewsEvents/Newsroom/PressAnnouncements/ucm560167.htm>). Only those CRC patients with MSI-L and MSS will be included in the efficacy analyses.

Ovarian cancer (OvC): WT1 expression is highly prevalent in OvC (Dupont et al, 2004). The degree of expression is high enough that pathologists routinely use IHC stains for WT1 with

a standardized convention for describing its expression to help distinguish epithelial ovarian cancers from other ovarian/fallopian tumors ([Al-Hussaini et al, 2004](#)). WT1 is a particularly sensitive and specific marker for serous ovarian cancer ([Acs, et al, 2004](#)).

Small-cell lung cancer (SCLC): WT1 expression has not been studied in SCLC as extensively as in non-SCLC (NSCLC), mainly due to the relative rarity of the former. Nonetheless, WT1 positivity is higher (40 to 83%) in SCLC versus NSCLC ([Babiak et al, 2014](#); [Menssen et al, 2000](#); [Oji et al, 2002](#); [Wang et al, 2013](#)). The activity of anti-PD1 agents in SCLC in the second line of therapy is reflected in ORR values of about 33 to 37% ([Ott et al, 2016](#); [Hellman et al, 2016](#); [Antonia et al, 2016](#); [Riess et al, 2016](#)).

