1.3.1.2.1. Metastatic Colorectal Cancer (Third/Fourth line)

Colorectal cancer (CRC) is a common disease, diagnosed in nearly 1.4 million people worldwide annually ([GLOBOCAN 2012](#)). In the United States, there are nearly 133,000 new diagnoses each year ([Key Statistics for Colorectal Cancer, 2016](#)). Approximately one-third of patients with CRC will develop metastatic disease. In most of these patients, the disease relapses and becomes refractory. The overall prognosis of patients with metastatic CRC has improved significantly, with average survival today being 30 months ([Formica and Roselli, 2015](#)), thanks to new research identifying different molecular subtypes of CRC. Although some patients with metastatic CRC can be cured, the disease remains incurable in most cases, clearly indicating a need for new therapies.

WT-1 expression has been documented to be expressed in between 70 to 90% of patients with CRC ([Miyata et al, 2007](#); [Oji et al, 2003](#); [Bejrananda et al, 2011](#)). Patients with

microsatellite-stable (MSS) molecular genetics make up between 80 to 90% of all CRC cases (Naboush et al, 2017; Diaz and Le, 2015). In this study, patients will have microsatellite (MS) instability (MSI) status tested in their primary tumors and will be classified as MSI- high (H) and -low (L) (Pawlik et al, 2004; Morán et al, 2010; Supek and Lerner, 2015; Goldstein et al, 2014). The focus will be on MSI-low tumors, but no entry selection will be applied based on this tumor feature. In several clinical trials in MSI-L CRC, anti-PD-1 agents have shown to induce 0 to 5% ORR (Link and Overman, 2016; <http://www.targetedonc.com/publications/targeted-therapies-cancer/2017/2017-february/immune-checkpoint-inhibitors-in-crc>; Boland and Ma, 2017; Myint and Goel, 2017; Overman et al, 2016; Segal et al, 2016; Bendell et al, 2016; Overman et al, 2016; Andre et al, 2017). This is in contrast to the significant activity of PD1 blockade in MSI-H CRC, the basis for the recent Food and Drug administration (FDA) approval of pembrolizumab in MSI-H cancers (including CRC) (<https://www.fda.gov/NewsEvents/Newsroom/PressAnnouncements/ucm560167.htm>). Only those CRC patients with MSS and MSI-H will be included in the efficacy analyses.

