Performance of the study design is evaluated on the basis of the probability of entering each decision zone for given true ORR values at the planned sample size within each cohort. Based on the performance characteristics summarized in [Table 11](#) through [Table 13](#), the sample sizes are adequate to address the study’s objectives.

Table 11 **Statistical Design Performance for CRC or OvC Cohorts of 20 Patients**

	Probability of Making Each Decision for a Given True ORR		
True ORR	Go (%)	Consider (%)	Stop (%)
20% (TV)	59	34	7
15%	35	47	18
10% (LRV)	13	48	39

CRC = colorectal cancer; ORR = overall response rate; OvC = ovarian cancer; LRV = lower reference value; TV = target value

Table 12 Statistical Design Performance for SCLC Cohort of 20 Patients

	Probability of Making Each Decision for a Given True ORR		
True ORR	Go (%)	Consider (%)	Stop (%)
40% (TV)	58	29	13
35%	40	36	25
30% (LRV)	23	36	42

ORR = overall response rate; LRV = lower reference value; SCLC = small cell lung cancer; TV = target value

Table 13 Statistical Design Performance for TNBC and AML Cohorts of 15 Patients

	Probability of Making Each Decision for a Given True ORR		
True ORR	Go (%)	Consider (%)	Stop (%)
25% (TV)	54	38	8
20%	35	48	17
15% (LRV)	18	50	32

AML = acute myeloid leukemia; ORR = overall response rate; LRV = lower reference value; TNBC = triple negative breast cancer; TV = target value

Calculations and simulations to determine decision boundaries and performance characteristics were performed using version 3.3.3 of the R software package (R Core Team).

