7.6.6. Go/No-Go and Futility Monitoring Guidelines

This study uses a Bayesian monitoring approach to guide decision-making using data on the primary efficacy endpoint (ORR) within each cohort. The specific criteria for making a Stop, Consider, or Go decision within each tumor-specific cohort at the planned sample size are derived using the following acceptable risks:

- 10% false stop risk: maximum acceptable probability that $ORR > TV$ given that a Stop decision is made.
- 20% false go risk: maximum acceptable probability that $ORR \leq LRV$ given that a Go decision is made

The Stop or Go decision criteria in each cohort are presented in Table 14.

Table 14 Decision Criteria for a Stop or Go Decision in Each Cohort at the Planned Sample Size

	Planned Sample Size	Target Value (TV)	Lower Reference Value (LRV)	Minimum Number of Responses for a Go Decision	Maximum Number of Responses for a Stop Decision
CRC	20	20%	10%	4	1
OvC	20	20%	10%	4	1
SCLC	20	40%	30%	8	5
TNBC	15	25%	15%	4	1
AML	15	25%	15%	4	1

AML = acute myeloid leukemia; CRC = colorectal cancer; ORR = overall response rate; OvC = ovarian cancer; LRV = lower reference value; SCLC = small cell lung cancer; TV = target value

Before reaching the planned sample size in a cohort, the posterior probabilities will be updated continuously after each patient or group of patients and will be used to determine, within each cohort, the predictive probability of a Stop decision at the planned sample size. If this predictive probability is $\geq 80\%$, then enrollment in that cohort may be stopped early for futility. The criteria for early futility stopping within each cohort are as follows:

CRC or OvC (N = number of patients currently enrolled in the cohort):

- If $N < 8$, there is insufficient data on ORR for a futility recommendation;
- If $N \geq 8$, futility stopping considered if no responses observed;
- If $N \geq 18$, futility stopping considered if ≤ 1 response observed.

SCLC (N = number of patients currently enrolled in the cohort):

- If $N < 3$, there is insufficient data on ORR for a futility recommendation;
- If $N \geq 3$, futility stopping considered if no responses observed;
- If $N \geq 7$, futility stopping considered if ≤ 1 response observed;
- If $N \geq 11$, futility stopping considered if ≤ 2 responses observed;
- If $N \geq 14$, futility stopping considered if ≤ 3 responses observed
- If $N \geq 17$, futility stopping considered if ≤ 4 responses observed

TNBC or AML:

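### The CRC Go/Stop counts, Table 11 and the futility points hold only if all 20 enrolled patients are analysed, yet MSI-H patients may enrol and are left out of the primary analysis

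*Combined protocol and SAP*

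**What the plan says.** Entry. Section 1.3.1.2.1 says of microsatellite status that "no entry selection will be applied based on this tumor feature". Section 4.1.2.1 lists no additional exclusion criteria for CRC, so MSI-H patients may enrol.

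Analysis. The synopsis (Analysis Sets) says "only those with MSS and MSI-L will be included in the primary efficacy analysis", and Section 7.5 says the same: "For CRC patients, only those with MSS and MSI-L will be included in the efficacy primary analysis". The CRC paragraph of the synopsis rationale puts it more widely: "Only those CRC patients with MSI-L and MSS will be included in the efficacy analyses". Section 1.3.1.2.1 disagrees: "Only those CRC patients with MSS and MSI-H will be included in the efficacy analyses".

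Numbers. Section 7.4 plans 20 CRC patients. Table 11 is titled "Statistical Design Performance for CRC or OvC Cohorts of 20 Patients" and Table 14 "Decision Criteria for a Stop or Go Decision in Each Cohort at the Planned Sample Size". The futility rule in Section 7.6.6 is headed "CRC or OvC (N = number of patients currently enrolled in the cohort", so its N counts enrolment, not analysis.

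Other sample sizes. Section 7.6.6 recalculates boundaries, with the same risk limits, for cohorts expanded by about 10 patients. It has no matching sentence for an analysed set smaller than planned.

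**The concern.** Every enrolled MSI-H patient counts toward the planned 20 and the futility N but is absent from the analysis that those numbers govern. The stated chances of Go, Consider and Stop then no longer describe the cohort, although Section 7.4 rests the adequacy of the sample size on them. There is also a practical ambiguity. With fewer than 20 analysed and exactly 3 responses, the printed count says Consider while the stated risk limits say Go. No sentence in the protocol says which applies.

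**Working it through.** **Inputs.** LRV 10%, TV 20%, planned N 20 (Section 7.4). Jeffreys prior Beta(0.5, 0.5), false-go limit 20%, false-stop limit 10%, futility threshold 80% predictive probability of Stop (Sections 7.6.1 and 7.6.6). MSS share of CRC 80-90% (Section 1.3.1.2.1). The MSI-H share is not given. The 10-20% that is not MSS includes MSI-L, so it is a ceiling for MSI-H; 2% and 5% are illustrative assumptions.

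**Formulas.** With r responses among n analysed, the posterior is Beta(0.5 + r, 0.5 + n - r). Go is the smallest r with P(ORR <= 10%) <= 0.20. Stop is the largest r with P(ORR > 20%) <= 0.10. Decision probabilities are exact binomial; futility uses the beta-binomial predictive distribution.

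**Reproducing the plan at n = 20.** P(ORR <= 10%) is 0.214 at 3 responses and 0.078 at 4, so Go is 4. P(ORR > 20%) is 0.032 at 1 response and 0.127 at 2, so Stop is 1. Go/Stop is 58.9%/6.9% at ORR 20% and 13.3%/39.2% at ORR 10%, matching Table 11. Predictive P(Stop) is 0.835 at 0/8 (0.798 at 0/7) and 0.852 at 1/18 (0.781 at 1/17), matching the printed 8 and 18.

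**One MSI-H patient, n = 19.** P(ORR <= 10% | 3 responses) = 0.190, inside the 20% limit, so the derived Go count is 3. P(ORR > 20% | 1 response) = 0.039, so Stop stays at 1.

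**By analysed n.** The Go >= 4 columns show the printed count kept; the derived columns apply the risk limits.

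| n | Derived Go / Stop | P(Go), Go >= 4 kept: ORR 20% / 10% | P(Go), derived: ORR 20% / 10% | P(Stop), derived: ORR 20% / 10% |
|---|---|---|---|---|
| 20 | 4 / 1 | 58.9 / 13.3 | 58.9 / 13.3 | 6.9 / 39.2 |
| 19 | 3 / 1 | 54.5 / 11.5 | 76.3 / 29.5 | 8.3 / 42.0 |
| 18 | 3 / 1 | 49.9 / 9.8 | 72.9 / 26.6 | 9.9 / 45.0 |
| 17 | 3 / 1 | 45.1 / 8.3 | 69.0 / 23.8 | 11.8 / 48.2 |
| 16 | 3 / 1 | 40.2 / 6.8 | 64.8 / 21.1 | 14.1 / 51.5 |
| 15 | 3 / 1 | 35.2 / 5.6 | 60.2 / 18.4 | 16.7 / 54.9 |
| 14 | 3 / 0 | 30.2 / 4.4 | 55.2 / 15.8 | 4.4 / 22.9 |
| 13 | 3 / 0 | 25.3 / 3.4 | 49.8 / 13.4 | 5.5 / 25.4 |
| 12 | 3 / 0 | 20.5 / 2.6 | 44.2 / 11.1 | 6.9 / 28.2 |

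Stop falls to 0 at n = 14 because P(ORR > 20% | 1 response) is 0.105 there, against 0.087 at n = 15.

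**How often this arises.** P(all 20 analysable) = (1 - q)^20 for MSI-H share q: 67% at 2%, 36% at 5%, 12% at 10%, 1% at the 20% ceiling. Averaged over the number analysed, keeping Go at 4 gives P(Go) at ORR 20% of 57%, 54%, 50% and 40%. Re-deriving gives P(Go) at ORR 10% of 18%, 23%, 24% and 21%.

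**Futility, final n = 20 minus MSI-H so far.** At 8 enrolled with no responses, predictive P(Stop) is 0.813 with one MSI-H patient and 0.786 with two. The printed trigger therefore fails the 80% test only if at least 2 of the first 8 are MSI-H: chance 1%, 6%, 19% and 50% at the four shares. At 18 enrolled with 1 response it stays above 0.80 with one to four MSI-H patients (0.844, 0.836, 0.826, 0.816).

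**The case against.** The best defence is that the rule is general. The synopsis and Section 7.6.1 update the prior with the available data, and the synopsis limits this to evaluable patients. The two risk limits then fix a boundary at any n, and Table 14 declares itself to be the case at the planned size. This stands in part: a reader might infer that the plan has no rule below 20, and the documents do not support that. What they lack is a sentence applying the limits to a smaller analysed set, when Section 7.6.6 has one for expanded cohorts. A general rule also does not rescue Table 11, because re-deriving moves P(Go) at ORR 10% from 13% to 29.5% at n = 19.

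Section 7.6 refers details to a SAP. No separate SAP text is available here, and it may settle the matter.

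The optional expansion is at the sponsor's discretion and not tied to MSI-H exclusions. Counting missing ORR as non-response (Section 7.6.1) does not cover patients excluded by design. It is fair that the criteria are non-binding and that a Consider result goes to further review and halts nothing.

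**Conclusion.** The point holds as a gap between what N counts and what is analysed. With one MSI-H patient the stated CRC probabilities are not delivered under either reading: P(Go) at ORR 20%/10% is 54.5%/11.5% or 76.3%/29.5%, against 59%/13%, and P(Stop) at ORR 20% is 8.3% against 7%. These conditional figures are exact. How far the cohort departs from Table 11 is uncertain, because it depends on an MSI-H share that the documents do not give. The effect is confined to Consider versus Go in one cohort, under non-binding criteria, with a small futility effect.

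Three stronger inferences should not be drawn. Keeping Go at 4 does not breach the false-go limit: P(ORR <= 10% | 4 responses) is 0.066 at n = 19, so 4 is merely no longer the smallest qualifying count. The bar on replacements in Section 4.2.3 sits under withdrawals and does not show that excluded MSI-H patients cannot be made up. The MSI-H wording in Section 1.3.1.2.1 does not make MSI-H patients part of the primary analysis; it is an evident slip against the synopsis and Section 7.5.

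**What to change.** **(a) Preferred.** State that the CRC planned N of 20 and the CRC futility N both count MSS/MSI-L patients, with MSI-H patients tabulated separately. All printed CRC figures then stand. Both definitions must change together. If 20 analysed is the target but futility N still counts enrolment, one MSI-H patient gives 0.798 at 8 enrolled with no responses and 0.781 at 18 enrolled with 1 response, both below 0.80.

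Cost: 20/(1 - q) is 21.05, 22.2 and 25.0 at an assumed 5%, 10% and 20% share, so 22, 23 or 25 enrolled. That is 2, 3 or 5 extra patients, within the existing allowance of about 10. Those totals yield at least 20 analysed with probability 91%, 81% and 62%, so enrolment should run until 20 MSS/MSI-L patients are in.

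**(b) With no added patients.** State that the 20% and 10% risk limits apply to the number of MSS/MSI-L patients analysed, count futility N the same way, and restate the CRC probabilities by analysed n. The boundaries are Go >= 4 at n = 20 and Go >= 3 at n = 12-19; Stop <= 1 at n = 15-20 and Stop at 0 at n = 12-14. The range must extend below 16, since at the 20% ceiling fewer than 16 are analysed with probability 37%. Futility points should be recomputed from the current analysed n and the expected final analysed n. The cost is accepting a higher P(Go) at the LRV for n = 13-19 than the 13.3% at n = 20.

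Separately, as an editorial matter, correct the MSI-H wording in Section 1.3.1.2.1 to agree with the synopsis and Section 7.5.
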